### 8.3 TIME PERIOD AND FREQUENCY FOR EVENT ASSESSMENT AND FOLLOW-UP

The occurrence of an AE or SAE may come to the attention of study personnel during study visits and interviews of a study participant presenting for medical care, or upon review by a study monitor. All AEs including local and systemic reactions not meeting the criteria for SAEs will be captured on the appropriate CRF. Information to be collected includes event description, time of onset, clinician's assessment of severity, relationship to study product (assessed only by those with the training and authority to make a diagnosis), and time of resolution/stabilization of the event. All AEs occurring while on study must be documented appropriately regardless of relationship. All AEs will be followed to adequate resolution.

Any medical condition that is present at the time that the participant is screened will be considered as baseline and not reported as an AE. However, if the study participant's condition deteriorates at any time during the study, it will be recorded as an AE. All AEs will be recorded in the data collection system throughout the study.

The PI will record all reportable events with start dates occurring any time after informed consent is obtained until the last day of study participation. At each study visit, the investigator will inquire about the occurrence of AE/SAEs since the last visit. Events will be followed for outcome information until resolution or stabilization.

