#### 10.3.5 SAFETY ANALYSES

Safety analysis will be performed on the DCTclock and Linus Platform safety analysis dataset. Treatment emergent adverse events, which are events that started or worsened during or after the first DCTclock or Linus Platform test, will be listed including start date of event and date and time of the test. The number of serious device related adverse events and number and percentage of subjects with at least one serious device related adverse event will be presented for each test.

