10.1 PRIMARY SAFETY VARIABLE

The study's primary safety endpoint is the incidence of subjects with serious device-related adverse events from enrollment to completion of the study. Safety will be analyzed on the Safety Population.

A table of treatment emergent adverse events (TEAEs), which are events that started or worsened during or after the first DCTclock or Linus Platform test, will be created. This table will present the number of TEAEs and the number and percent of subjects with at least one TEAE in each visit category (visit 1, between visits, visit 2, or at any time) with which the TEAE is associated.

TEAES will be categorized as follows at each visit, with the number of TEAEs and number and percent of subjects with at least one TEAE presented for each category at each visit:

- Any TEAE,
- TEAE by severity (mild/moderate/severe; if a subject has more than one TEAE, then only the events in the most severe category experienced will be tabulated, and the subject will be placed in the most severe category experienced),
- Relationship (not related or related, where related is further broken down by the categories of possible, probable, definite) to each of the following (if a subject has more than one TEAE, then only the events in the most related category experienced will be tabulated, and the subject will be placed in the most related category experienced):
 - DCTclock-pen (the denominator at Visit 1 and between visits will be those subjects who underwent testing with the pen at Visit 1; the denominator at Visit 2 will be those subjects who underwent testing with the pen at Visit 2)
 - DCTclock-tablet/drawing tests,
 - Decision making/reaction time,
 - Balance/walking,
 - PHQ-9/Lifestyle questionnaire (Visit 2 only),
 - Speech elicitation assessments,
 - Eye tracking assessments (Visit 2 only),
 - Other study assessments,
 - Concomitant medication,
 - Intercurrent intervention/procedure,
 - Pre-existing condition/underlying disease,
 - Intercurrent condition,
 - Incidental finding,
 - Unknown,
 - Other.
- Whether the TEAE led to study discontinuation or not,
- Whether the TEAE is a serious adverse event (SAE or not),
- Whether the TEAE led to death or not.

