TEAEs will also be presented in a listing. This listing will include the randomization group, site, subject ID, visit number, date of visit, date of TEAE onset, study day number of onset, date TEAE resolved, number of study days from start to resolution of TEAE, whether it is an SAE or not (if so the reasons for the SAE will be listed after 'Y' in the SAE column), whether or not the study resulted in study discontinuation, outcome, severity, relationship to any study device/test component (any instance in which the TEAE is at least possibly related will be listed and in parentheses will be the exact noted relationship i.e. balance/walking (probable)) and action taken (in any instance in which

the action taken requires a specification, the specification will be written in parentheses i.e. medication (Ativan)).

A listing for device observations (observations associated with the Linus Platform devices) will be presented. This listing will display the randomization group, site, subject ID, description of the observation, observation #, date and study day of observation, whether or not the observation is related to an AE, whether or not the observation is related to Linus platform device components (and if so, which one(s)), time the observation occurred, type of observation, action taken to address the observation/outcome.

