Group XX	XX	XXX-XXX	XXXXXX	XXXXXX XX/XX/XXXX	XX/XX/XXXX	XX/XX/XXXX XX	Y/N	Y/N	XXXXXX	XXXXXX	XXXXXX	XXXX
		XXX-XXX	XXXXXX	XX/XX/XXXX	XX/XX/XXXX	XX/XX/XXXX XX	Y/N	Y/N	XXXXXX	XXXXXX	XXXXXX	XXXX
												...

*Only AEs that have the onset time of “during assessments” or “between assessment visits” are included in this listing

Any specified reasons for SAEs will be listing in the SAE column after ‘Y’

Any instance in which the AE is at least possibly related will be listed and in parentheses will be the exact noted relationship i.e. balance/walking (probable)

**In any instance in which the action taken requires a specification, the specification will be written in parentheses i.e. medication (Ativan)
This listing will be ordered by randomization group, then site, then subject ID.**

Table #
Device Observations
Safety Population

[figure not shown]
Randomization Group	Site	Subject ID	Description	Observation #	Date of Observation (Study Day of Observation)	Related to AE	Related to Linus Platform Device Components	Time Observation Occurred	Type of Observation	Action Taken to Address Observation/ Outcome
Group X	XXX	XXX-XXX XXXXX	XXXXXX	XXXXXX	XX/XX/XXXX (XX)	Y/N	XXXXXX	XXXXX: XXXXX	XXXXX	XXXXXX
		XXX-XXX XXXXX	XXXXXX	XXXXXX	XX/XX/XXXX (XX)	Y/N	XXXXXX	XXXXX: XXXXX	XXXXX	XXXXXX
		XXX-XXX XXXXX	XXXXXX	XXXXXX	XX/XX/XXXX (XX)	Y/N	XXXXXX	XXXXX: XXXXX	XXXXX	XXXXXX
Group X	XXX	XXX-XXX XXXXX	XXXXXX	XXXXXX	XX/XX/XXXX (XX)	Y/N	XXXXXX	XXXXX: XXXXX	XXXXX	XXXXXX
		XXX-XXX XXXXX	XXXXXX	XXXXXX	XX/XX/XXXX (XX)	Y/N	XXXXXX	XXXXX: XXXXX	XXXXX	XXXXXX

This listing will be ordered by randomization group, then site, then subject ID.

Table #			
Exploratory Analysis: MMSE, RBANS and Linus Individual Tests and Overall Score Descriptives			
Validation Population			
	Visit 1	Visit 2	Total
MMSE			
Mean ± SD (N)		N/A	
Median (Min, Max)		N/A	
RBANS			
Mean ± SD (N)			
Median (Min, Max)			
Linus Total Score			
Mean ± SD (N)			
Median (Min, Max)			
Linus Platform Drawing Test: Pre-test			
Mean ± SD (N)			
Median (Min, Max)			
Linus Platform Drawing Test: Pathfinding			
Mean ± SD (N)			
Median (Min, Max)			
Linus Platform Drawing Test: Symbol			
Mean ± SD (N)			
Median (Min, Max)			
Linus Platform Drawing Test: Connect			
Mean ± SD (N)			
Median (Min, Max)			
Linus Platform Drawing Test: Tracing			
Mean ± SD (N)			
Median (Min, Max)			
Linus Platform Decision Making and Reaction Time Test: Simple Reaction Time			
Mean ± SD (N)			
Median (Min, Max)			

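### The TEAE listing carries an onset-label restriction that is not in the SAP's TEAE definition and is not applied to the TEAE table, so the two displays can differ on which events they show

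*SAP*

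**What the plan says.** SAP section 10.1 (Primary Safety Variable) defines TEAEs as events "which are events that started or worsened during or after the first DCTclock or Linus Platform test". The definition covers both new onset and worsening and states no upper time limit. The summary table counts TEAEs "in each visit category (visit 1, between visits, visit 2, or at any time"). The same section then says "TEAEs will also be presented in a listing" and attaches no onset condition.

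The listing shell in SAP Appendix A, titled as a listing of treatment-emergent events in the Safety Population, has this footnote: "Only AEs that have the onset time of “during assessments” or “between assessment visits” are included in this listing". The TEAE table shell in the same appendix has footnotes on severity and relationship only.

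Protocol 10.3.5 uses the same TEAE definition and says the events "will be listed including start date of event and date and time of the test". Protocol 8.3 sets the recording window as "start dates occurring any time after informed consent is obtained until the last day of study participation" and adds that "if the study participant's condition deteriorates at any time during the study, it will be recorded as an AE". SAP section 12, which lists changes from the protocol, mentions only software.

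**The concern.** The footnote selects on where onset falls. The definition selects on onset or worsening relative to the first test. These are different rules, so the table and the listing are specified on event sets that need not agree.

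The listing has a particular role. The primary safety endpoint is the incidence of subjects with serious device-related events. The TEAE table shell gives seriousness and relationship as separate blocks of rows and never crosses them. Only the listing shell puts the SAE indicator and the related component on one row. An event missing from the listing may be counted in the table, but no SAP shell would show whether that same event was both serious and device-related.

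**Working it through.** The plan states no figure to reproduce. The check compares the rules and adds up the schedule.

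**1. Compare the rules, with the footnote read as an added condition on TEAEs**

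| Event | TEAE under SAP 10.1? | Carries a listed onset label? |
|---|---|---|
| Starts after the last Visit 2 test, same day | Yes | No: assessments are over and no visit follows |
| Starts after consent but before the first test, then worsens after it | Yes, by worsening | Not if onset precedes whatever the first label covers |
| Starts during a test, or between the visits | Yes | Yes |

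The first two rows can be lost from the listing while staying in the table.

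**2. Size of the Visit 2 gap.** In protocol 7.3.2 the last scheduled item is a Linus reaction time test, and the visit ends participation. Protocol 8.3 stops recording new events on the last day of participation. The gap is therefore the remainder of one day per subject.

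**3. Size of the pre-test window at Visit 1** (durations from protocol 7.3.1)

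- Screening: 15 + 5 + 1 + 1 + 10 + 3 + 5 = 40 min, as stated.
- Study assessments: 20 + 1 + 5 + 15 + 5 + 5 + 30 = 81 min, as stated.
- AEs are recorded only after consent (15 min), so the screening time at issue is 40 − 15 = 25 min.
- The neurological assessment (20 min) and randomization (1 min) come before DCTclock: 20 + 1 = 21 min, inside the block the protocol calls study assessments.
- Maximum from consent to the first DCTclock test: 25 + 21 = 46 min.

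This window matters in two ways, depending on what *during assessments* covers. If the label is narrow, an AE that starts in the window and later worsens is dropped. If it is broad, and is used alone to pick rows, an AE confined to the window is admitted although it is not a TEAE.

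**4. Could a reader of the listing see the error?** The shell shows visit date, onset date and study day. Under SAP 7.6 every Visit 1 event is Day 0. It shows neither onset time nor test time, so Visit 1 events cannot be ordered against the first test. Protocol 10.3.5 calls for the time of the test, and protocol 8.3 includes time of onset among the data collected.

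**5. Expected number of events.** The earlier pen study in protocol 2.3.1 had 37 AEs, one of them serious, in 435 participants: 37 / 435 = 0.085 per participant. If that rate held here (an assumption, since that study's window was 1 to 4 weeks and this one's is 3 to 5), there would be 0.085 × 175 ≈ 15 to 0.085 × 200 ≈ 17 events in all. Those in the gaps above would be a small part of that.

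**The case against.** The strongest reply is that the footnote only narrows. The listing is titled as TEAEs and SAP 10.1 says it lists TEAEs, so an event must meet the definition and also carry a label. On that reading no event from before device use can enter. This stands. A reader might infer that the labels replace the definition and that the listing admits pre-device events; the documents do not establish that. It would happen only if a programmer used the labels as the selection rule.

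A reader might also count 60 of the 121 Visit 1 minutes as exposed (40 screening plus 20 neurological assessment). That includes consent, before which no AE is recorded. The supported ceiling is 46 minutes, or 21 if the label follows the protocol's split between screening and study assessments.

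Other points on that side also stand:

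- The labels look like CRF categories, but the CRFs are cited and not reproduced, so their options and completion rules are unknown.
- Protocol 8.3 records deterioration of a condition present at screening as an AE, which may get its own in-study onset label. The worsening loss is therefore narrower than it first looks.
- The visit date is in the shell, so only the clock time of the test is missing.
- Protocol 10.3.5 plans counts of serious device-related events for each test, and SAP 5.2 commits to analyses named in the protocol. The listing is thus not the only planned output combining the two attributes. It is the only SAP shell that does so.

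None of this removes the mismatch. A restriction that appears in neither governing text still excludes events that those texts include.

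**Conclusion.** The point holds as a minor inconsistency within the SAP. As written, the footnote can drop from the listing two kinds of event that meet the SAP 10.1 definition: those starting after the last Visit 2 test on the final day, and AEs that began after consent but before the first test and then worsened. Admission of events from before the first test is possible only under a particular implementation, within at most 46 scheduled minutes.

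The number of events affected is likely to be very small. A reader might infer that the primary safety incidence is compromised. The documents do not support that: the footnote governs the listing alone, and neither the TEAE table nor the counts planned in protocol 10.3.5 are filtered by it. What is at stake is that table and listing reconcile, and that each event's seriousness and relationship can be read together.

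The conclusion assumes that the two labels have their ordinary meaning and that visits follow the scheduled order.

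**What to change.** - Delete the footnote from the listing shell.
- Select listing rows with the same TEAE flag, derived from SAP 10.1, as the table uses.
- Add two columns: AE onset time, which protocol 8.3 collects, and the time of the test, which protocol 10.3.5 requires. Both are needed to order same-day Visit 1 events; the visit date is already shown.
- If the CRF turns out to record onset only as a category, state in SAP 10.1 how that category, together with any worsening information, is used to apply the definition.

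The cost is a shell edit and a small programming change, with no new data if onset is recorded as a time. DCTclock data are time-stamped (protocol 2.1 and 13.4). Whether onset clock time is on the CRF should be checked first, because the category fallback would be less precise.

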##### **Linus Platform drawing tasks**

Linus is developing a series of drawing-based tablet tests administered with the Apple iPad and Apple Pencil. Just like with DCTclock, an analysis of drawing behavior will be conducted to identify early indications of cognitive change. An iPad application captures, encrypts, and transmits the encrypted data to Linus' HIPAA compliant servers. These drawing-based tasks include:

- Pre-test: An exercise involving copying waves that is administered before completing the other tablet tests (including DCTclock-tablet) with the only goal of making the subject comfortable with drawing using the Apple Pencil and the iPad.
- Pathfinding test: A series of mazes to be completed as quickly and accurately as possible.
- Symbol test: Keys of symbol-digit pairs are provided followed by prompts with empty boxes where the subject is asked to input the appropriate response as quickly as possible.
- Connect test: The subject is instructed to connect a set of circles as quickly as possible according to a pre-established pattern.
- Tracing test: The subject is asked to trace a line with both their dominant and non-dominant hand.

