#### Visit 1 (Day 1) ~120 minutes total

Visit 1 Screening (40 mins)	Time Estimate
Obtain informed consent of potential participant verified by signature on written informed consent form approved by the IRB. Consent must be obtained before any study assessments are completed.	15 mins
Demographics and review of medical history and current medications	5 mins
Assessment of impairment of the dominant hand	1 min
Assessment of recreational drug or alcohol use	1 min
MMSE	10 min
Hamilton-Veale Contrast Sensitivity	3 mins
Purdue Peg Board	5 mins

If a subject screen fails at any step, they will not complete the remaining assessments; eligible subjects complete the following study assessments.

Visit 1 Study Assessments (81 mins)	Time Estimate
Brief neurological assessment	20 min
Randomized to receive DCTclock-pen or DCTclock-tablet	1 min
DCTclock-pen or DCTclock-tablet	5 mins
Linus Platform drawing tests with list learning	15 mins
Linus Platform decision making and reaction time assessments	5 mins
Linus Platform gait and balance assessments	5 mins
RBANS	30 mins

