11.2 TEST-RETEST RELIABILITY ANALYSES

Subjects will undergo cognitive testing with both the Linus Platform tests and the reference standard RBANS twice, where the second examination will be three to five weeks after the first examination. Test-retest reliability of both individual Linus Platform tests and the combined Linus score will be compared to the test-retest reliability of the RBANS. For the analysis, subjects who no longer satisfy the inclusion/exclusion criteria prior to the second examination will be excluded.

For, the individual Linus Platform scores, the developed Linus score, and the reference standard RBANS, agreement analyses will be carried out as follows:

- Agreement between the first and second measurements will be measured. A scatter plot of measurement 2 vs. measurement 1 will be generated, superimposed with a line of identity. An unweighted Deming regression (where the variance of the measurement error is determined by the two measurements that were collected 3-5 weeks apart) will be carried out to determine the y-intercept, slope and their two-sided 95% CIs. The ICC will also be determined.
- A hypothesis test of the slope vs. 1 and of the y-intercept vs. 0 will be carried out. Specifically, the following hypothesis test will be carried out: $H_0: \beta_0 = 0$ vs. $H_1: \beta_0 \neq 0$ and $H_0: \beta_1 = 1$ vs. $H_1: \beta_1 \neq 1$ where β_0 and β_1 are the y-intercept and slope, respectively, from the Deming unweighted regression. Each of these will be carried out at a two-sided 0.05 level of significance.

The Evaluable Population will be used for these analyses.

In addition to the above, descriptive statistics (N, mean, standard deviation, median, minimum and maximum) of the Visit 1, Visit 2 and the difference between Visit 1 and Visit 2 (calculated as Visit 1

minus Visit 2) will be presented for the RBANS score, for the Linus total score and for the Linus Platform individual test scores.

Figures will display the above described plots and the associated statistics (y-intercept and slope and their Cis, ICC, estimates of β_0 and β_1 from the Deming regression, and the p-values from the test of the Deming null hypotheses).

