Linus Platform Decision Making and Reaction Time Test: Procedural Reaction Time			
Mean ± SD (N)			
Median (Min, Max)			
Linus Platform Decision Making and Reaction Time Test: Go/No-Go			
Mean ± SD (N)			
Median (Min, Max)			
Linus Platform Decision Making and Reaction Time Test: PHQ-9			
Mean ± SD (N)			
Median (Min, Max)			
Linus Platform Speech Elicitation Tasks: Complex Picture Description			
Mean ± SD (N)			
Median (Min, Max)			
Linus Platform Speech Elicitation Tasks: Category Naming			
Mean ± SD (N)			
Median (Min, Max)			
Linus Platform Speech Elicitation Tasks: Object Recall			
Mean ± SD (N)			
Median (Min, Max)			
Linus Platform Speech Elicitation Tasks: Sentence Reading			
Mean ± SD (N)			
Median (Min, Max)			
Linus Platform Speech Elicitation Tasks: Sustained Phonation			
Mean ± SD (N)			
Median (Min, Max)			

Linus Platform Speech Elicitation Tasks: Diadochokinetic Rate			
Mean ± SD (N)			
Median (Min, Max)			
Linus Platform Speech Elicitation Tasks: Story Recall			
Mean ± SD (N)			
Median (Min, Max)			
Linus Platform Speech Elicitation Tasks: List Learning			
Mean ± SD (N)			
Median (Min, Max)			
Linus Platform Eye Tracking-Based Memory Assessments			
Mean ± SD (N)	N/A		
Median (Min, Max)	N/A		
Linus Platform Gait and Balance Assessment			
Mean ± SD (N)			
Median (Min, Max)			
Linus Platform Lifestyle Questionnaire			
Mean ± SD (N)	N/A		
Median (Min, Max)	N/A		

Figure #
MMSE vs. Linus Score at Visit 1

This figure will be repeated for all other individual Linus platform test scores, as well as for RBANS at Visit 1 vs. Linus (Individual Platform Test or Overall Linus Score) at Visit 1 and RBANS at Visit 2 vs. Linus (Individual Platform Test or Overall Linus Score) at Visit 2

Table # Exploratory Analysis: Test-Retest Reliability Evaluative Population			
	Visit 1	Visit 2	Difference between Visit 1 and 2 (Visit 1 – Visit 2)
RBANS			
Mean ± SD (N)			
Median (Min, Max)			
Overall Linus Score			
Mean ± SD (N)			
Median (Min, Max)			
Linus Platform Drawing Test: Pre-test			
Mean ± SD (N)			
Median (Min, Max)			
Linus Platform Drawing Test: Pathfinding			
Mean ± SD (N)			
Median (Min, Max)			
Linus Platform Drawing Test: Symbol			
Mean ± SD (N)			
Median (Min, Max)			
Linus Platform Drawing Test: Connect			
Mean ± SD (N)			
Median (Min, Max)			
Linus Platform Drawing Test: Tracing			
Mean ± SD (N)			
Median (Min, Max)			
Linus Platform Decision Making and Reaction Time Test: Simple Reaction Time			
Mean ± SD (N)			
Median (Min, Max)			

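### Linus test-retest reliability pools the two randomised sequences, so any residual clock-device effect would lower the ICCs of four drawing tests and the overall Linus score

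*SAP*

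**What the plan says.** SAP 11.2 compares the test-retest reliability of the individual Linus tests and the combined Linus score with that of RBANS. It states "Agreement between the first and second measurements will be measured", by scatter plot and Deming regression, and adds "The ICC will also be determined". The Deming intercept and slope are tested against 0 and 1: "Each of these will be carried out at a two-sided 0.05 level of significance". On the data set it says "The Evaluable Population will be used for these analyses". No sequence term or stratum appears.

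The matching shell in SAP Appendix A, "Exploratory Analysis: Test-Retest Reliability Evaluative Population", has a Visit 1 column, a Visit 2 column and one for "Difference between Visit 1 and 2 (Visit 1 – Visit 2)". It has no group columns. By contrast, the shells for the DCTclock overall score and composite scales are laid out by randomised group, and SAP 9.2 models test order for the DCTclock score difference.

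Protocol 4.1 gives Group 1 the pen clock and then the tablet clock, and Group 2 the reverse. The Visit 1 schedule in Protocol 7.3.1 has a step "Randomized to receive DCTclock-pen or DCTclock-tablet", then the clock test (5 minutes), then the Linus drawing tests (15 minutes). Protocol 7.3.2 keeps the clock directly before the drawing tests at Visit 2.

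Protocol 6.1 also describes a wave-copying Pre-test, given ahead of the other tablet tests (the tablet clock among them), "with the only goal of making the subject comfortable with drawing using the Apple Pencil and the iPad".

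**The concern.** On a tablet visit the subject draws one clock and copies another with the Apple Pencil on the iPad, then starts the Linus drawing tests on the same hardware. On a pen visit the clock is drawn on paper. The iPad drawing done just before the battery therefore differs between a subject's two visits, and the direction depends on randomised group.

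If the extra drawing changes performance at all, the change enters one group's visit difference with a plus sign and the other's with a minus sign. Equal allocation cancels it in the mean but not in the spread. A pooled ICC then counts a feature of the crossover as measurement error of the Linus test. RBANS is not a tablet test and comes later in both visits, after the drawing, reaction-time and gait tests, so it is less exposed. The exploratory comparison of Linus with RBANS could be tilted against the drawing tests for a reason unrelated to their reliability.

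**Working it through.** The plan gives no power or precision figure for test-retest reliability, so there is none to reproduce. Its 41-subject calculation is for the Bland-Altman endpoint and does not enter here.

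**Inputs from the documents.** Two sequences, 1:1 (Protocol 10.4.1); 175 subjects expected for analysis (Protocol 4.1); the device order and schedule described above.

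**Assumptions.** The true ICC, rho, and the device effect w (tablet visit minus pen visit, in units of the SD of one score). The documents give neither, so ranges are shown. The effect is taken as equal at both visits.

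**Model.** Score = subject + error, plus w/2 on tablet-clock visits and minus w/2 on pen-clock visits. Subject variance is rho and error variance is 1 - rho, so the total is 1. Pooling two equal sequences gives:

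- variance at each visit: 1 + w²/4
- covariance between visits: rho - w²/4
- pooled ICC = (rho - w²/4) / (1 + w²/4)
- variance of the visit difference: 2(1 - rho) + w², so its SD is multiplied by sqrt(1 + w²/(2(1 - rho)))

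**Worked cases at rho = 0.80.**

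- w = 0.2: ICC = (0.80 - 0.01)/1.01 = 0.782; SD ratio = sqrt(0.44/0.40) = 1.049.
- w = 0.5: ICC = (0.80 - 0.0625)/1.0625 = 0.694; SD ratio = sqrt(0.65/0.40) = 1.275.

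| w | Pooled ICC, rho 0.70 | Pooled ICC, rho 0.80 | Pooled ICC, rho 0.90 | SD ratio, rho 0.80 |
|---|---|---|---|---|
| 0.1 | 0.696 | 0.796 | 0.895 | 1.012 |
| 0.2 | 0.683 | 0.782 | 0.881 | 1.049 |
| 0.3 | 0.663 | 0.760 | 0.858 | 1.107 |
| 0.5 | 0.600 | 0.694 | 0.788 | 1.275 |

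**Simulation** (176 subjects for an even split, 1,500 runs, rho = 0.80, two-way absolute-agreement ICC):

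| w | Pooled ICC (sampling SD) | Sequence-adjusted ICC | Deming slope | Mean Visit 1 - Visit 2 |
|---|---|---|---|---|
| 0 | 0.797 (0.028) | 0.798 | 1.003 | -0.0006 |
| 0.2 | 0.781 (0.029) | 0.800 | 0.998 | 0.0011 |
| 0.5 | 0.693 (0.038) | 0.799 | 1.005 | -0.0004 |

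The pooled values match the formula, and removing the sequence-by-visit shift restores the true ICC. The Deming slope and mean difference do not move.

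**Which scores are exposed.** The shell has 20 rows. A stylus effect can reach Pathfinding, Symbol, Connect and Tracing and, through them, the overall Linus score: 5 rows. The Pre-test row precedes the day's other stylus use. The reaction-time, PHQ-9, speech and gait rows involve no stylus drawing.

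**Unequal effects.** With effects w1 at Visit 1 and w2 at Visit 2, the Visit 1 minus Visit 2 change is shifted by w1 in the tablet-first group and by -w2 in the pen-first group. The group contrast is w1 - (-w2) = w1 + w2, which equals 2w only if the two are the same.

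**The case against.** The strongest reply is that the protocol already deals with stylus familiarity. The Pre-test exists for that purpose and comes before the other tablet tests whichever clock version is used. A reader might infer that pen-visit subjects reach the drawing tests with no stylus warm-up; Protocol 6.1 does not support that. The contrast is the Pre-test plus two tablet clock drawings against the Pre-test alone. This stands, and it makes a large w less plausible. It does not make w zero, because nothing in the documents shows that the Pre-test uses up the effect.

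A second reply is that no effect size is documented, that a loss of about 0.02 at w = 0.2 is smaller than the ICC's sampling SD of about 0.03, and that every subject has already done the full drawing battery by Visit 2, so any effect may fade. All of this stands. It is why the point is conditional, and why a constant w is an assumption.

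A third reply is that the difference in shell layout is not itself an inconsistency: pen against tablet is the comparison in the effectiveness shells, and visit against visit is the comparison here. That is fair. The case rests on the design, not on the layout.

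Finally, the endpoint is exploratory, with no success threshold and no formal test of the Linus ICC against the RBANS ICC. That limits the consequence.

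**Conclusion.** The point holds as a conditional one. SAP 11.2 and its shell pool two sequences in which the preceding clock device switches in opposite directions. Any residual effect that runs the same way at both visits would lower the ICC and widen the SD of the difference for four drawing tests and the overall Linus score. At a true ICC of 0.80, the pooled value is 0.78 for w = 0.2 SD and 0.69 for w = 0.5 SD. These figures rest on an assumed w, equal at both visits, and on 1:1 sequences.

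A reader might go further and conclude that pooling demonstrably biases Linus reliability in general, or invalidates the Deming tests. The documents support neither. They give no evidence that w differs from zero, most rows of the shell cannot be affected by a stylus effect, and under this model the mean difference and Deming slope are not materially shifted. What remains is a possible downward bias in a stated exploratory comparison, removable at almost no cost.

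**What to change.** For Pathfinding, Symbol, Connect, Tracing and the overall Linus score, with RBANS as comparator:

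- Add Group 1 (pen first) and Group 2 (tablet first) columns to the test-retest shell, beside the total.
- In SAP 11.2, report the ICC and the SD of the difference from a model with visit and visit-by-randomised-group terms, alongside the pooled figures.
- Report the between-group contrast in Visit 1 minus Visit 2 change with its 95% CI, described as the sum of the two visits' device effects. This puts a measured size on an effect that is now unknown.

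No change to the Deming analysis is needed. The cost is SAP and shell wording, minor extra programming and one degree of freedom per score. Randomised group is already in the data. If there is no device effect, the adjusted and pooled ICCs will be essentially the same (0.798 against 0.797 in the simulation at w = 0).
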